Randomization. Our biostatistician will oversee the process of randomization of subjects to either the NO-ASPIRATE or usual care group. He will develop a blocked randomization procedure, using different sized blocks, to ensure balanced assignment without being able to predict group assignment.¹⁶⁶ Because many subjects will be intubated with the specialized SS-ETT (about 65% from historical data), we will stratify randomization by type of ETT to ensure that approximately half of those with and without the SS-ETT are randomly assigned to each group. Stratification will help to address type of tube as a potential confounding variable, and will allow for secondary sub-group analysis. A member of the study team not involved in data collection will place group assignments for each type of ETT in numbered, sealed, opaque envelopes. Upon enrollment, study personnel will identify the type of ETT, and open the appropriate envelope to determine group assignment. Only study team members who provide the intervention will know the subjects' assigned groups. ICU personnel, as well as subjects and family members, will be blinded to the assignment.

Intervention. Following enrollment, the RA will collect baseline data, implement the assigned intervention (NO-ASPIRATE or usual care/sham), and collect specimens. The RA will then implement the intervention as designated by study arm every 4 hours. *Figure 4 summarizes the procedures for each group.*

To control for possible differences in usual oral care practices, the RA will perform oral cleansing and suctioning with a suction swab after delivering the NO-ASPIRATE or sham intervention using the hygiene components from the oral care kit. The RA will also perform tooth brushing every 12 hours. Oral antisepsis will be done after obtaining specimens for α -amylase. Some subjects may require additional oral suctioning for secretion management; staff will use the available tonsil suction device for oral suctioning in-between the scheduled interventions and document in the medical record. Additional necessary oral suctioning will be recorded and controlled for, if applicable.

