NO-ASPIRATE Intervention. The NO-ASPIRATE intervention involves enhanced suctioning of the mouth and oropharynx every 4 hours with an oropharyngeal suction catheter. The catheter is 8.25" (21 cm) long (see Figure 2D) and is one that we tested in the simulated setting as being most effective in removing oropharyngeal secretions.⁹⁹ *Figure 5 compares secretion removal with a suction swab (usual care) versus the oropharyngeal suction catheter. This length and pliability of the oropharyngeal suction catheter facilitate manipulation of the catheter around the ETT to reach secretions in the oropharynx. In contrast, suction swabs and tonsil suction devices are shorter and rigid, and do not reach secretions that pool in the oropharynx.*

During the intervention, the oropharyngeal suction catheter will be repositioned to reach both sides of the mouth and the oropharynx. Suctioning will be done using standard suction pressures until secretions are no longer audible or visible, for a duration of about 45 seconds.²⁵ ¹²¹ We have performed this procedure in previous studies without any adverse issues, such as gagging or oral trauma.^{25,93}

However, subject response will be observed and the procedure will be stopped if intolerance is noted.

Usual Care/Sham Intervention. A usual care/sham intervention will be delivered to those in the usual care group. Trained RAs will insert the suction catheter into the subject's mouth and mimic the suction procedure for 45 seconds without occluding the suction port. The usual care/sham intervention will be done every 4 hours.

Data Collection. Data will be collected at enrollment and at regular intervals (Table 1), including demographic and physiological data to describe the sample and *test equivalence between groups*. We will also collect data related to factors that might influence microaspiration and development of VAC to assist in interpretation of findings and be used as possible covariates in statistical analyses. *We anticipate having 4 to 6 subjects enrolled at a time. This estimate was based on consultation with [name] and designed to ensure adequate time to deliver the intervention, enroll new subjects, and record data from the medical record.* Additionally, at this rate of accrual, laboratory will be able to regularly process the α -amylase assays.

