Paired specimens of oral and tracheal aspirates for α -amylase. The RA will obtain an oral specimen for α -amylase at enrollment and every 12 hours (concurrently with a tracheal aspirate) to compute the tracheal/oral ratio. Oral secretions will be collected into a trap during the NO-ASPIRATE or usual care/sham intervention. Following this procedure, a tracheal aspirate will be obtained for detection of α -amylase. Although Weiss detected α -amylase in BAL specimens up to 72 hours post intubation, others have suggested more frequent collection.^{46,97} Obtaining specimens every 12 hours will provide longitudinal data regarding microaspiration, and facilitate identification of clinical factors that contribute to its occurrence. The RA will suction the subject's ETT per standard procedure (closed ETT suction with hyperoxygenation via the ventilator before the procedure) to retrieve tracheal secretions into a specimen trap. We tested these procedures in a preliminary study.⁹³ Since ETT suctioning should be done based on identified need,¹²¹ the RA will assess the subject for cues identifying suctioning need before obtaining the specimen: audible crackles over the trachea, sawtooth

pattern on the ventilator flow waveform, cough, high peak inspiratory pressure, visible secretions, or changes in oxygen saturation.^{85,122} *If suctioning is not indicated at the scheduled time, the RA will collaborate with the subject's nurse to notify the RA if suctioning is clinically indicated within a 2-hour period to ensure complete collection of samples. Time of specimen collection (or omissions) will be noted. The usual care oral antisepsis done for all subjects will be done AFTER specimen collection to prevent contamination.* All oral and tracheal specimens will be frozen to -20° C until the assays are run. A compact medical lab freezer, used solely for purposes of this study, will be purchased and located on or near one of the study units for easy storage. Specimens will be regularly transported on ice to the APH Specialty Diagnostic Laboratory.

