The NO-ASPIRATE or usual care/sham intervention will be administered by a member of the research team every 4 hours. The decision for this interval was based on the volume of oral secretions measured in our preliminary studies,²⁵ and non-experimental quality improvement studies that implemented oropharyngeal suctioning at 4- and 6-hour intervals.^{64,94} Concurrently with delivery of the interventions, paired specimens of oral and tracheal secretions will be obtained at baseline and every 12 hours for assays of α -amylase. Tracheal specimens will be obtained based on the subject's need for ETT suctioning.

List any collaborating sites where human subjects research will be performed, and describe the role of those sites and collaborating investigators in performing the proposed research. Explain how data from the site(s) will be obtained, managed, and protected.

Subjects will be patients in one of the ICUs at Orlando Regional Medical Center. The study team has extensive experience conducting clinical studies in these units. Three of our co-investigators are employees at the site. [name] is chairman of the corporate Critical Care Committee, which will facilitate communication across units. As Director for the Center for Nursing Research, [name] helps to establish collaborations between the university and hospital. [name] oversees the APH Specialty Diagnostic Laboratory where the α -amylase assays will be run. Additionally, [name] has an appointment as a Nurse Scientist at the agency, which also facilitates collaboration and the ability to conduct research in the setting.

Data will be recorded in electronic means on password-protected computers. The subject's medical record number will be used to retrieve study-related data from the electronic medical record (EMR). All subjects will be issued a unique code that will be recorded in the research files. All data will be de-identified for final analysis and findings will be reported in aggregate. A key, pairing the medical record number and unique identification code, will be kept separate from all data in a locked file in [name] research office at UCF. Access to this information will be limited and only on a "need-to-know" basis.

B. SOURCES OF MATERIALS

Describe the research material obtained from living individuals in the form of specimens, records, or data.

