The probability of adverse consequences to participants is minimal. Removal of secretions is an independent nursing action that is routinely done but not per evidence-based protocol. We propose to enhance secretion removal through a protocol-driven procedure done every 4 hours. We do not anticipate that this frequency of oral suction poses a risk to subjects as nurses have the option to suction as needed with devices that they prefer to use, usually a suction swab or tonsil suction device. A recent study conducted in Asia tested a device that was kept in the mouth for continuous suction, and reported no adverse issues.²² We have observed that patients may awaken during oral care interventions, but that they fall back to sleep immediately after it is done. We have performed this procedure (NO-ASPIRATE) to obtain specimens in previous studies without any adverse issues, such as gagging or oral trauma.^{25,93} However, subject response will be observed as part of ongoing monitoring.

Oral care kits are standard for each patient, with supplies for oral suction, cleansing every 4 hours, and tooth brushing every 12 hours. We will use the same brand of oropharyngeal catheter that is packaged in the kits on a scheduled every-4-hour basis to those in the NO-ASPIRATE group.

All subjects will get usual care to prevent microaspiration, including head of bed elevation, management of enteral feedings, assessment of readiness to wean from MV, and management of ETT cuff pressure within recommended ranges. Many subjects will be intubated with the specialized subglottic suction ETT.

Trained members of the research team will implement the NO-ASPIRATE or usual care/sham interventions and collect data related to the study; all RAs will be experienced practitioners in management of patients on MV. Education and training is scheduled before beginning data collection and regularly throughout the study.

We will purchase all study-related supplies, including the oropharyngeal suction catheters, sputum traps, and materials needed to run the α -amylase assays. No additional costs will be associated with participation.

Where appropriate, describe alternative treatments and procedures, including the risks and potential benefits of the alternative treatments and procedures, to participants in the proposed research.

No alternate treatments are identified.

D. RECRUITMENT AND INFORMED CONSENT

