Subjects in both groups will have oral suctioning done every 4 hours. The NO-ASPIRATE group will be suctioned with the oropharyngeal catheter while the usual care/sham group will be suctioned with the swab. We will use the same type of oral hygiene equipment (catheter and swab) readily available in the oral care kits for the NO-ASPIRATE and usual care/sham interventions. We will regulate the suction pressure for oropharyngeal and ETT suction within recommended ranges. Subjects may awaken during the intervention. In our pilot work, 25% of subjects awakened during the procedure; however, they returned to their resting state immediately after the procedure. Any oral intervention has the potential to increase gagging; however, we have not noted that to be an issue with the oropharyngeal suction catheter in our preliminary studies.

Paired oral and tracheal specimens will be obtained for analysis of α -amylase. Tracheal aspirates will be obtained every 12 hours during a scheduled NO-ASPIRATE or usual care/sham intervention if clinical assessment indicates that the subject needs to be suctioned through the ETT. Suctioning will be done per standard procedures using the closed ETT suction system and recommended suction pressures. The subject will be hyperoxygenated via the ventilator before the procedure. ETT suctioning is regularly necessitated by the intubated patient and these same standards are followed when the patient is suctioned by the nurse or

respiratory therapist. We have used the same procedures in preliminary studies. Oral specimens will be obtained during the NO-ASPIRATE or usual care/sham intervention.

Existing standards of care to prevent microaspiration will be continued by the nursing and respiratory care staff. These interventions include head of bed elevation, management of enteral feedings, management of the subglottic suction ETT (if patient is intubated with the SS-ETT), maintaining the ETT cuff pressure within recommended ranges (20 and 30 cm H₂O), daily assessment of readiness to extubate, and oral antisepsis.

All data will be coded to ensure confidentiality of information. Members of the research team will be trained in measurement techniques and safety precautions for all interventions and related procedures. They will demonstrate proficiency in a simulated setting prior to initiation of the study, and on a regular basis.

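### The plan does not show how the control-arm oral specimen is obtained, and one plausible reading ties sampling device and site to arm in the Aim 3 tracheal/oral ratio

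*Combined protocol and SAP*

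**What the plan says.** Two places in the combined protocol and SAP set the timing of the oral specimen. The section Paired specimens of oral and tracheal aspirates says "Oral secretions will be collected into a trap during the NO-ASPIRATE or usual care/sham intervention", with the tracheal aspirate taken afterwards. Human Subjects, section E (Protection Against Risk), repeats it: "Oral specimens will be obtained during the NO-ASPIRATE or usual care/sham intervention". Neither names a device.

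The section Usual Care/Sham Intervention has the assistant place the catheter in the mouth and "mimic the suction procedure for 45 seconds without occluding the suction port".

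Swab suction is described in three ways:

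- The Intervention section makes it a later step in both arms: "the RA will perform oral cleansing and suctioning with a suction swab after delivering the NO-ASPIRATE or sham intervention".
- The Figure 4 caption lists, for each arm, the assigned step, then specimen collection, then swab suction as usual care.
- Section E instead presents the swab as the control arm's suction: "The NO-ASPIRATE group will be suctioned with the oropharyngeal catheter while the usual care/sham group will be suctioned with the swab".

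For enrolment, Human Subjects section A says: "Concurrently with delivery of the interventions, paired specimens of oral and tracheal secretions will be obtained at baseline and every 12 hours".

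The oral value is the denominator of the tracheal/oral ratio. Analysis 3.1 compares that ratio between arms by GEE, and Data Analysis sets alpha at 0.05 for all analyses.

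**The concern.** A ratio compared between arms needs a denominator measured the same way in both. In the NO-ASPIRATE arm the route is clear: real suction with a catheter moved over both sides of the mouth and the oropharynx. In the control arm the specimen is to be collected during a step that only imitates suction, so the text does not show how secretions reach the trap.

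The obvious way to fill the gap is to use the swab for controls. The section NO-ASPIRATE Intervention says that swabs do not reach secretions pooled in the oropharynx. On that reading, device and site are completely confounded with arm. The Aim 3 ratio could then differ between arms with no difference in aspiration, or a real difference could be hidden. Covariate adjustment cannot separate two factors that coincide exactly.

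**Working it through.** **Step 1. Set the sections side by side.**

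| Reading | Fits | Conflicts with | Consequence |
|---|---|---|---|
| (a) Sham as written, port open | Usual Care/Sham Intervention | The instruction to collect oral secretions in both arms | No control-arm oral specimen, so no control ratio |
| (b) Swab supplies the control specimen | Section E on what the control group is suctioned with | Intervention section and Figure 4 caption, where the swab is separate from the assigned step | Device and site tied to arm in the Aim 3 denominator |
| (c) Port occluded at specimen times | Collection during the assigned step | Usual Care/Sham Intervention | Devices match, but controls receive real catheter suction |

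Under (c), specimens fall every 12 hours and sessions every 4 hours. Since 12/4 = 3, about one control session in three would include real suction. That dilutes the suction contrast; it does not bias the ratio's denominator.

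**Step 2. Look for a described control-arm method.** The only earlier collection described is the active procedure. Section C says "We have performed this procedure (NO-ASPIRATE) to obtain specimens in previous studies without any adverse issues". The pilot summary under Preliminary Studies mentions no sham.

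**Step 3. Effect on the ratio under reading (b).** Let the control oral reading be k times what the catheter would have given. With no true effect, the apparent NO-ASPIRATE/control ratio is (T/O) ÷ (T/kO) = k. The documents give no k and no SD for the ratio, and the Power Analysis section has no figure for Aim 3, so there is no plan figure to reproduce.

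**Step 4. A purely illustrative calculation.** Assume k = 1.25, an SD of the log ratio between 1 and 2, one value per subject and a two-sided 5% test. Noncentrality = ln(k)/(SD × √(2/n)).

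- n = 200 per arm (the final 400 split 1:1): 0.223 × 10 = 2.23 at SD 1 and 1.12 at SD 2. The chance of a significant difference from the device alone is 0.61 to 0.20.
- n = 92 per arm, because a log ratio needs detectable tracheal amylase and the first pilot tracheal sample was positive in 6 of 13 (46% of 200 = 92): 0.223 × √46 = 1.51 and 0.76. The chance is 0.33 to 0.12.
- k = 1: 0.05, the nominal level.

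The spread shows how far the answer depends on assumed inputs. It does not estimate this trial's error rate.

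**Step 5. What enrolment data could show.** All 13 pilot subjects had oral amylase, so log oral values should generally be available. With 200 per arm, the 95% margin on k is exp(1.96 × SD × √(2/200)), where SD is that of log oral amylase: a factor of 1.10 at SD 0.5, 1.22 at SD 1 and 1.48 at SD 2. These SDs are also assumptions.

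**The case against.** The strongest reply is that this is operational detail kept elsewhere. The Intervention section says that Figure 4 summarises each group's procedures, and its image is not available. Personnel Training and Fidelity promises an Operations Manual and simulation training in specimen collection. The Figure 4 caption lists specimen collection as its own item, in the same words for both arms, which is compatible with a common method. The section on paired specimens also says that the procedures were tried in a preliminary study. This stands as a limit: a method may exist, and one cannot conclude that the specimen is unobtainable. It does not remove the conflict. The manual was still to be written, the remark about earlier testing describes no sham collection, and the caption names no device and does not fit the two statements that place collection during the assigned step.

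A second reply is that reach is not concentration. The assay reports activity per millilitre from a 10 µl sample, so lower yield alone would not bias the value. That is right, and nothing in the documents shows that k differs from 1.

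A reader might infer that Aim 3 is biased in a known direction, or that its false-positive rate is inflated by a stated amount. The documents support neither. Bias needs reading (b) and also a difference in amylase concentration by device or site, and no data on that are given.

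**Conclusion.** The concern holds in limited form. Stated rules conflict, the control-arm oral sampling method is not shown in the available text, and one of three readings ties device and site to arm in an outcome tested at alpha 0.05. The size and direction of any resulting bias are unknown, and there may be none.

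The sampling bias is confined to Aim 3, which the plan calls secondary and exploratory. H1.1 and H1.2 use tracheal values and VAC uses ventilator and record data, so none of them takes in the oral value. A reader might extend the point to the primary aim; the documents do not support that as a measurement bias. Reading (c) would raise a separate question about the intervention contrast.

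The conclusion rests on the text alone, without the Figure 4 image or the Operations Manual. It is worth correcting, but it does not threaten the main result.

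**What to change.** Reconcile the sections Intervention, Usual Care/Sham Intervention, Figure 4, Paired specimens and Human Subjects section E. Specify one oral-sampling device, one site and one time point relative to the assigned step, identical in both arms from the enrolment specimen onward, without altering the suction contrast. If the Operations Manual already names such a method, carry it into the protocol.

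The cost is revised wording and retraining of the research assistants. A common method may also give a smaller or less oropharyngeal sample in one arm.

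If arm-specific sampling has already been used:

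- Compare enrolment oral amylase between the randomized arms as a check on k.
- Report the between-arm ratio as descriptive, and rely on the tracheal values.
- Treat change from enrolment on the log scale as a sensitivity analysis only. A constant device factor cancels if it was also present at enrolment. But the Intervention section lists specimen collection after the first assigned step, so the enrolment values may not be pre-treatment, and a device factor may vary over time.
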